Statistical Plan, Results and Conclusions for:

A Clinical Decision Support Tool for Electronic Health Records (Official Title)

NCT number 02697643

Document Date: August 9, 2018

Analytic Approach.

Primary Analytic Approach. We are interested in learning whether participants in the intervention condition, BH-CDS, as compared to the control condition, treatment as usual, have (1) greater access to wraparound services, (2) more treatment visits, and (3) longer retention in treatment. As secondary hypotheses, we will examine whether the intervention condition, as compared to the control condition, will be associated with significantly (1) greater psychosocial outcomes, and (2) reduced drug use. A mixed model analytic approach was chosen for its ability to: adjust for individual-level covariates; take into account nesting of clients within counselors; and efficiently maximize the correlated nature of the repeated measures data in the design. Each mixed model will include fixed effects (condition, time and condition-by-time); random effects (clients nested within counselors); repeated measures variation (time); as well as potential counselor-level demographic covariates (e.g., experience level) and client-level demographic covariates (i.e., age). Non-significant covariates will be removed systematically. After arriving at the final model for each analysis, the condition-by-time effect will be examined for significance. In the presence of a significant condition-by-time effect, Bonferroni corrected post-hoc contrasts will be conducted to test for differences between conditions on mean change from baseline to one month follow-up and baseline to three month follow up

Analyses by Hypothesis

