Primary Hypothesis 1: Clients in the experimental condition will have significantly greater matched evidenced-based and wraparound services than clients in the control condition. To address this hypothesis, a chart review was conducted to enumerate services received during the study period. The percentage of services that clients in the experimental condition received from the list of tailored recommendations was calculated. We then compared this percentage to the percentage of services that clients in the control condition would have received had they been in the experimental condition and received tailored recommendations. Because all clients participating in the study completed the PDE, we were able to determine which set of recommendations clients in the control condition would had received had they been in the experimental.

Primary Hypothesis 2: Clients in the experimental condition will have greater engagement in treatment than clients in the control condition. Engagement in treatment was calculated by dividing the number of treatment sessions attended during the study period by the total number of scheduled treatment sessions (i.e., opportunities for treatment), a sum of treatment sessions attended plus the number of scheduled sessions that the client did not show up for (no-show). An independent samples T-test was utilized to determine whether there were statistically significant differences between participants in the experimental and control groups with respect to treatment engagement.

Primary Hypothesis 3: Clients in the experimental condition will have less frequent use of substances than clients in the control condition. Use of substances was measured by the number of relapses during the study period. An independent samples *T*-test was conducted to evaluate whether participants number of relapses differed significantly between the experimental and control groups.

Primary Hypothesis 4: Clients in the experimental condition will have greater biopsychosocial functioning than clients in the control condition. Biopsychosocial functioning was captured by the seven ASI-MV composite scores. The ASI-MV was administered at baseline, 1-month follow-up and 3-month follow-up. Change in the ASI-MV composite scores was evaluated over time and across participant groups with a repeated measures mixed model.

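### Hypothesis 3 compares raw relapse counts by a plain t-test, without observed time or counselor clustering, so the result is open to bias if observation differed by arm

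*SAP*

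**What the plan says.** In the SAP, Analyses by Hypothesis, Primary Hypothesis 3 states: "Clients in the experimental condition will have less frequent use of substances than clients in the control condition". The outcome is then fixed as a count: "Use of substances was measured by the number of relapses during the study period". The test is an independent-samples t-test, "conducted to evaluate whether participants number of relapses differed significantly between the experimental and control groups". The text gives no denominator, rate, offset, covariate or rule for clients who leave early. It does not say how relapses were ascertained, what the study period was for them, or whether counting stopped when a client left treatment.

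Three other places bear on this:

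- The Primary Analytic Approach lists "longer retention in treatment" among the main aims and reduced drug use among the secondary ones. It chooses mixed models partly because clients are nested within counselors.
- Primary Hypothesis 2 does use a denominator. Engagement is found by "dividing the number of treatment sessions attended during the study period by the total number of scheduled treatment sessions".
- Data sources and time points are given for other outcomes only. For Hypothesis 1, "a chart review was conducted to enumerate services received during the study period". For Hypothesis 4, "The ASI-MV was administered at baseline, 1-month follow-up and 3-month follow-up".

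**The concern.** Frequency of use is a rate, and a raw count measures a rate only if everyone is observed for the same time. This trial hopes to keep experimental clients in treatment longer. If a relapse can be recorded only while a client is in care or can be reached, success on retention gives that arm more time in which relapses can be counted. A client who leaves early contributes few recorded relapses and looks like a success. A real reduction in the relapse rate could then be hidden or, with a large enough difference in observed time, appear as an increase.

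The second weakness is separate. The t-test treats clients as independent, which departs from the SAP's own stated approach. With 140 clients and 24 counselors (140 ÷ 24 = 5.8 clients per counselor on average), the nesting is not negligible by design. How far it affects the standard error depends on how conditions were spread across counselors and how alike one counselor's clients are. The document quantifies neither.

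**Working it through.** **Inputs from the SAP.** Arm sizes are 47 control and 93 experimental; 47 + 93 = 140, which agrees with the stated total. The document gives no power, effect-size or alpha figure for Hypothesis 3, so there is nothing of its own to reproduce. It gives no relapse means, standard deviations, observation times or retention figures.

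**Algebra.** If relapses are counted only during observed time, and the rate does not depend on how long a client stays, then

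expected count ratio = rate ratio × ratio of mean observed time.

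The benefit is fully masked when the observed-time ratio equals 1 ÷ rate ratio:

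- rate ratio 0.9: 1 ÷ 0.9 = 1.11
- rate ratio 0.8: 1 ÷ 0.8 = 1.25
- rate ratio 0.7: 1 ÷ 0.7 = 1.43

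Beyond these points the direction reverses. If the observed-time ratio is 1, the count ratio equals the rate ratio.

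**Simulation, first set of assumptions.** 47 vs 93 clients; control rate 0.5 relapses per month; gamma-Poisson counts with dispersion 1; a 3-month window; two-sided 0.05; 20,000 runs. Observed times are mean months, control vs experimental. The rate analysis divides by person-time and uses a robust variance.

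| True rate ratio | Observed time | Expected counts | Significant benefit, t-test | Significant benefit, rate analysis | Significant harm, t-test |
|---|---|---|---|---|---|
| 1.0 | 2.0 vs 2.0 | 1.00 vs 1.00 | 2.9% | 2.7% | 2.1% |
| 1.0 | 2.0 vs 2.2 | 1.00 vs 1.10 | 1.0% | 2.7% | 4.3% |
| 1.0 | 2.0 vs 2.5 | 1.00 vs 1.25 | 0.3% | 2.8% | 11.5% |
| 0.8 | 2.0 vs 2.5 | 1.00 vs 1.00 | 2.9% | 14.6% | 2.1% |
| 0.7 | 3.0 vs 3.0 | 1.50 vs 1.05 | 33.5% | 32.6% | 0.0% |
| 0.7 | 2.0 vs 2.0 | 1.00 vs 0.70 | 26.9% | 27.6% | 0.1% |
| 0.7 | 2.0 vs 2.2 | 1.00 vs 0.77 | 17.1% | 27.8% | 0.1% |
| 0.7 | 2.0 vs 2.5 | 1.00 vs 0.875 | 8.2% | 28.1% | 0.6% |

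With equal observation the two analyses agree. The t-test goes wrong only when observed time differs by arm.

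**Simulation, second set of assumptions.** One relapse per 30 days, dispersion 0.5, a 90-day window, exponential dropout, and a true rate ratio of 0.65 for power:

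- 45 vs 47 days (47 ÷ 45 = 1.04): false harm about 3%, against about 2% with equal time; power about 34%, against about 40%.
- 45 vs 49.5 days (ratio 1.10): false harm 5%, power 28%.
- 39 vs 57 days (57 ÷ 39 = 1.46): false harm 33%; power about 4%, against 37% at 39 vs 39 days. Here the expected count ratio is 0.65 × 57 ÷ 39 = 0.95.
- A full 90 days for everyone: total type I error about 5%, power 72%.

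Neither simulation includes counselor clustering or dropout related to relapse.

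**The case against.** A reader might infer that longer retention must have raised the experimental arm's relapse count, whatever the source of the data. The document does not support that. Retention in treatment is not the same as time under observation. A client who leaves treatment may still attend the 1-month and 3-month follow-ups, and an interview with a fixed look-back gives both arms equal exposure. The study period can also be read as one common window. The source and window for relapses may be set out in the protocol, which is not shown. This objection stands, and it makes the bias conditional.

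A reader might also infer that the reported null on relapses was caused by better retention. The SAP's Conclusion says no impact on retention was demonstrated, and no apparent harm is reported, so nothing shows that the bias operated. Equal observation is not shown either. None of Hypotheses 1 to 6 analyses length of stay, and Hypothesis 2 is a share of sessions attended: a client who attends every session and then leaves early scores 100%.

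It is tempting to add that a client who never stops using cannot relapse. That depends on a definition of relapse that the document does not give.

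Finally, substance use does not rest on this count alone. The ASI-MV alcohol and drug composites are modelled over time under Hypothesis 4 and were reported as not significant. This limits the consequences but does not repair the Hypothesis 3 test.

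**Conclusion.** The concern holds in conditional form. The stated test does not match a hypothesis about frequency, takes no account of observed time in a trial that aims to lengthen retention, and drops the counselor nesting that the SAP says it accommodates.

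The possible bias is governed by the observed-time ratio. For a gap of 5 to 10%, false harm stays at or below about 5% under both sets of assumptions, although power falls, for example from 27% to 17% at a rate ratio of 0.7 and a 10% gap. For gaps of 25 to 45% the distortion is large: false harm of about 12 to 33%, and most of the power lost. With a common, fully ascertained window it is nil. All these percentages rest on assumed rates, dispersion and observation times; only the masking thresholds follow from algebra alone, and they too require that recording stops when observation stops.

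Until observation time is shown, the null result for Hypothesis 3 should not be read as evidence of no difference in relapse rate.

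**What to change.** 1. State how relapses were ascertained, over what window, and when counting stopped for a client who left. Report days under observation by arm.
2. Analyse relapses with a negative binomial (or quasi-Poisson) model, with log(days under observation) as offset, condition as fixed effect and counselor clustering. Report the rate ratio with its 95% CI.
3. If every client was observed for the same window, show this. The offset is then constant and only the count model and the clustering change.
4. Because the Hypothesis 3 result is already reported, show the t-test beside the new analysis and label the latter as added afterwards.
5. Keep the ASI-MV alcohol and drug composites under Hypothesis 4 as supporting evidence. Substituting them for the Hypothesis 3 outcome now would be a post hoc outcome change, and they too depend on follow-up being completed.

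The cost is a few lines of SAP text and a short re-analysis. Observation days must come from chart or follow-up dates, and the document does not say that these are held. The offset does not correct informative dropout, where clients leave because they relapse, so that limitation should be stated with the result.

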Primary Hypothesis 5: Clients in the experimental condition will have greater cost effectiveness than clients in the control condition. Costs of services provided to the participating clients in the experimental and control conditions during the study time period was estimated in the following way. Services received by each client as documented during the chart review process for Hypothesis 1 above. The cost of each service was estimated using the CPT code for that service (e.g., group psychotherapy = 90853). To establish consistent costs, estimates of cost for each CPT code were derived from Medicare reimbursement estimates in Massachusetts using online tools (e.g., https://www.findacode.com). While not precise, use of Medicare reimbursement is often used to get a general and relative sense of service costs across states. This is especially useful for comparing groups (e.g., experimental versus control), rather than attempting to generate precise cost estimates. Costs per individual were summed and averaged for t-test comparison between experimental and control groups. If patient outcomes are superior for one group, this test would determine whether the outcome difference is associated with greater or lesser costs.

Primary Hypothesis 6: Counselors in the experimental condition will report satisfaction with the BH-CDS Program. At the end of the study, participating counselors were asked to complete a satisfaction survey, which included both open-ended questions and Likert-type rating scale questions. Due to the small number of counselors in the experimental and control groups, formal statistical significance testing was not conducted. Instead, these data were analyzed descriptively. Open-ended text were subject to qualitative thematic analysis.

Results

Counselor Participants. A total of 24 counselors at four outpatient substance abuse treatment facilities around the United States participated in the current study.

Client Participants. One hundred and ninety patients completed consent forms and completed baseline surveys. Of these, 140 participants were fully enrolled into the study (completed the PDE, counselors obtained recommendations from the BHCDS system, participants completed the baseline survey). Forty-seven participants were randomized into the control, TAU, condition and 93 were randomized into the experimental condition. Demographics were relatively similar across the experimental and control conditions.

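### The ASI-MV analysis (Hypothesis 4) compares change from baseline without adjusting for the baseline composite: valid under randomisation, but less precise than the collected data allow

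*SAP*

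**What the plan says.** The SAP's Primary Analytic Approach sets one structure for all mixed models: "Each mixed model will include fixed effects (condition, time and condition-by-time); random effects (clients nested within counselors); repeated measures variation (time"). The decision rule follows: "After arriving at the final model for each analysis, the condition-by-time effect will be examined for significance". If that effect is significant, Bonferroni-corrected contrasts are to "test for differences between conditions on mean change from baseline to one month follow-up and baseline to three month follow up".

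The only covariates described are demographic: "as well as potential counselor-level demographic covariates (e.g., experience level) and client-level demographic covariates (i.e., age"), and covariates that are not significant are removed.

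Under Analyses by Hypothesis, Primary Hypothesis 4 gives the visits: "The ASI-MV was administered at baseline, 1-month follow-up and 3-month follow-up". Baseline is thus part of the repeated outcome. The model is described as "Change in the ASI-MV composite scores was evaluated over time and across participant groups with a repeated measures mixed model".

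On allocation, the Results (Client Participants) state: "Forty-seven participants were randomized into the control, TAU, condition and 93 were randomized into the experimental condition".

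**The concern.** A condition main effect next to a condition-by-time interaction gives each arm its own baseline mean. With complete data, the interaction contrast at a visit is then exactly the between-arm difference in mean change. If clients were randomised, both arms have the same expected baseline mean, so estimating two of them spends precision without gaining validity.

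The same section says the mixed model was chosen partly to make efficient use of the correlation between repeated measurements. The chosen contrast does not achieve that. All seven composites get wider intervals and lower power than the same data could give.

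A second consequence is conditional on the sample. A chance baseline difference between 47 and 93 clients carries into the change contrast through regression to the mean.

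**Working it through.** The SAP states no SD, correlation, effect size or power for this hypothesis, so there is no figure of its own to reproduce.

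**Inputs.** Arm sizes are 47 and 93 (Results, Client Participants). Visits are baseline, 1 month and 3 months (Primary Hypothesis 4). Assumed: SD 1 at every visit, and baseline-to-follow-up correlation rho of 0.5, 0.6 or 0.7.

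**Step 1, one visit, complete data.**
- 1/47 + 1/93 = 0.0213 + 0.0108 = 0.0320; its square root is 0.179.
- Difference in change: variance = 2(1 − rho) × 0.0320.
- Baseline-adjusted difference: variance = (1 − rho²) × 0.0320.
- Ratio = (1 − rho²) / [2(1 − rho)] = (1 + rho)/2.

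The excess is 2(1 − rho) − (1 − rho²) = (1 − rho)², so only part of the baseline noise is added.

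| rho (assumed) | SE, change | SE, adjusted | Variance ratio | 140 / ratio |
|---|---|---|---|---|
| 0.5 | 0.179 | 0.155 | 0.75 | 187 |
| 0.6 | 0.160 | 0.143 | 0.80 | 175 |
| 0.7 | 0.139 | 0.128 | 0.85 | 165 |

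The last column is the number of clients the change analysis would need to match the adjusted analysis of 140. At rho 0.5 the change contrast is no more precise than ignoring baseline altogether (SE 0.179).

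**Step 2, counselor effects and missing follow-up.** Exact generalised least squares variances were computed for the SAP model and for a model with a common baseline mean. The settings were three visits, compound symmetry, 24 counselors, rho 0.3 to 0.7, counselor ICC 0 to 0.10, assignment by client or by counselor, and 0 or 20% missing follow-up. The ratio ran from 0.61 (rho 0.3, ICC 0.10, by client, none missing) to 0.92 (rho 0.7, ICC 0.10, by counselor, 20% missing). With rho limited to 0.5 to 0.7 it ran from 0.72 to 0.92. The covariate form was not computed separately under clustering. With complete data and no counselor effect it has the variance in Step 1.

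**Step 3, the overall condition-by-time test.** This test comes first in the SAP. Take time as categorical (2 df), compound symmetry, complete data, and arm effects d1 and d3 at the two follow-ups. Up to a common factor, the information is:
- SAP model: 2(d1² − d1·d3 + d3²) / 3
- Baseline-adjusted: [(1 + rho)(d1² + d3²) − 2·rho·d1·d3] / (1 + 2·rho)

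SAP information divided by adjusted information:

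| Effect pattern | Formula | rho 0.5 | 0.6 | 0.7 |
|---|---|---|---|---|
| One follow-up only | 2(1+2rho)/[3(1+rho)] | 0.89 | 0.92 | 0.94 |
| Twice as large at 3 months as at 1 month | 2(1+2rho)/(5+rho) | 0.73 | 0.79 | 0.84 |
| Equal at both | (1+2rho)/3 | 0.67 | 0.73 | 0.80 |

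The loss is therefore 6% to 33%.

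**Step 4, chance imbalance.** A baseline difference of one standard error (0.179 SD) shifts the expected change contrast by (1 − rho) × 0.179, which is 0.09 SD at rho 0.5.

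**The case against.** The strongest reply is that nothing here is an error. A repeated-measures model with condition, time and interaction is conventional, unbiased on average over randomisations, and keeps its type I error. That stands. A reader might infer from the chance-imbalance argument that the Hypothesis 4 results are biased, but the document does not support it. It reports no baseline ASI-MV comparison, so no actual imbalance is shown, and it describes demographics as similar between arms.

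A second reply is that the gain is not automatically free. A common baseline mean assumes the analysed arms are comparable at baseline. The SAP reports that 190 clients completed baseline surveys but only 140 were fully enrolled, a status that required counselors to have obtained recommendations from the system. It does not say whether this selection came before or after allocation. Its references to counselors in the experimental and control groups also leave open that assignment followed counselors. This stands against putting the constrained model first. It does not count against adjusting for baseline as a covariate, although no adjustment would repair selection after allocation.

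A third reply is that a single 15% to 25% reduction in variance does not describe the planned procedure, which starts with the overall interaction test and includes a counselor effect. This also stands, so the wider ranges in Steps 2 and 3 should be quoted with it.

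Finally, the document already contains the results, so this is not a mere change of wording in a prospective plan.

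**Conclusion.** The point holds as a weakness of efficiency. The SAP's ASI-MV contrast is a difference in change scores with baseline free by arm and no baseline covariate, and it is less precise than a baseline-adjusted contrast for any rho below 1. For a single visit the adjusted variance is 0.75 to 0.85 of the SAP variance at rho 0.5 to 0.7, given complete data and equal variances. It is roughly 0.61 to 0.92 over the wider settings examined. For the overall test the information lost is 6% to 33%. All of these rest on an assumed rho, and the gain at a single visit is modest if rho is high.

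A reader might go further and conclude that low precision explains the non-significant composites, or that the one reported difference is an artefact of baseline imbalance. The document gives no estimates, intervals or baseline composites from which either could be shown.

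**What to change.** Model the 1- and 3-month composites as outcomes, with the baseline composite as a prespecified covariate exempt from removal for non-significance. Keep the counselor random effect, and report the arm difference with its interval at each follow-up for all seven composites. If an overall test is kept, it should be the joint arm effect at the two follow-ups. Once baseline leaves the outcome, a condition-by-time term only asks whether the arm difference changes between 1 and 3 months.

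A constrained model with a common baseline mean is an alternative only if the selection from 190 to 140 came before allocation, which the authors should state.

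No new data are needed. The cost is refitting seven models and labelling the output as a sensitivity re-analysis made after the results were reported, beside the original analysis and not in its place.

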Primary Hypothesis 1: Clients in the experimental condition will have significantly greater matched evidenced-based and wraparound services than clients in the control condition. Results test indicated no significant difference for experimental and control groups.

Primary Hypothesis 2: Clients in the experimental condition will have greater engagement in treatment than clients in the control condition. T-tests indicated that the experimental and control groups did not differ with respect to treatment engagement.

Primary Hypothesis 3: Clients in the experimental condition will have less frequent use of substances than clients in the control condition. The mean number of relapses during the study period for the experimental group was not significantly different from the control group.

Primary Hypothesis 4: Clients in the experimental condition will have greater biopsychosocial functioning than clients in the control condition. Results for psychiatric status, medical status, alcohol use, family status, or drug use were not significant. Employment status results suggest that participants in the experimental, CDS, condition had significantly fewer legal problems than controls.

Primary Hypothesis 5: Clients in the experimental condition will have greater cost effectiveness than clients in the control condition. The CDS program did not yield significantly different costs effectiveness than the control group.

Primary Hypothesis 6: Counselors in the experimental condition will report satisfaction with the BH-CDS Program. Overall, counselors found it easy to complete the CDS program and reported that their clients' reaction was "neutral" or "positive" (no counselors reported a negative client reaction).

Counselors exposed to the tailored recommendations, reported that they were easy to understand, easy to integrate into the client's treatment plan, and useful for informing treatment decisions and were more likely to incorporate the tailored recommendations into future treatment planning.

Conclusion

Although the use of clinical decision support is promising, the present effort was unable to empirically demonstrate a direct impact on outcome, retention, amount of service delivered or cost. Further research on the impact of clinical decision support for substance use treatment is warranted.

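### Primary Hypothesis 5 compares Medicare-priced service costs with no term for the cost of BH-CDS itself, so it cannot support a conclusion on the program's cost effectiveness

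*SAP*

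**What the plan says.** The hypothesis (SAP, Analyses by Hypothesis, Primary Hypothesis 5) reads: "Clients in the experimental condition will have greater cost effectiveness than clients in the control condition". The costing method is introduced with "Costs of services provided to the participating clients in the experimental and control conditions during the study time period was estimated in the following way" and has four parts:

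- Resource use: "Services received by each client as documented during the chart review process for Hypothesis 1 above".
- Unit cost: "The cost of each service was estimated using the CPT code for that service".
- Prices: "estimates of cost for each CPT code were derived from Medicare reimbursement estimates in Massachusetts using online tools".
- Test: "Costs per individual were summed and averaged for t-test comparison between experimental and control groups".

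The SAP concedes that these prices are rough but holds that they serve for comparing groups. If one group has better outcomes, "this test would determine whether the outcome difference is associated with greater or lesser costs".

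The Results entry for the same hypothesis reads: "The CDS program did not yield significantly different costs effectiveness than the control group". It gives no means, SDs, interval or p-value. The Conclusion adds that no direct effect on cost could be shown.

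**The concern.** The hypothesis and the reported result are about a program; the quantity analysed is the cost of charted services. The costing rule is set out from resource use to test, so this is something the SAP fixes, not a detail left to a protocol. No step adds a software or licence share, training, or counselor time spent obtaining and applying recommendations.

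The SAP's caveat on price accuracy does not cover this. Rough Medicare prices apply to both arms alike, which is why they can still serve a comparison. A cost that BH-CDS adds to TAU falls on one side of the comparison that the hypothesis names.

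At stake is the reading of the result. A null on service cost may be taken to mean that adopting BH-CDS is cost-neutral, and a favourable service-cost difference would have been taken as a saving before the program had been paid for.

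**Working it through.** **Inputs.** Control 47, experimental 93, enrolled 140 (SAP, Results, Client Participants); 47 + 93 = 140. The SAP states no mean cost, cost SD, program cost or significance level for this hypothesis, so it has no figure to reproduce. Everything below is in units of the per-client cost SD, with a common SD and a two-sided 5% level as assumptions.

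**Precision of the comparison.**

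- SE = SD × √(1/47 + 1/93) = 0.179 SD.
- 95% half-width = t(0.975, 138) × SE = 1.977 × 0.179 SD = 0.354 SD.

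**Effect of an omitted cost.** Let c be the mean program cost per experimental client, incremental to TAU. Treated as a constant, it raises the experimental mean by c and leaves the SD and SE unchanged. Leaving it out therefore lowers the experimental-minus-control difference by c and shifts t by c / 0.179 in favour of the experimental arm. For c = 0.1 SD the shift is 0.1 / 0.179 = 0.56.

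The last column is the chance that the test shows the experimental arm as significantly cheaper when true total costs are equal, Φ(c/0.179 − 1.96). The nominal value is 2.5%.

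| Assumed c (SD) | Shift in t | Chance of a false saving |
|---|---|---|
| 0.05 | 0.28 | 4.6% |
| 0.10 | 0.56 | 8.1% |
| 0.20 | 1.12 | 20% |
| 0.30 | 1.68 | 39% |
| 0.50 | 2.79 | 80% |

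An omitted cost of about 0.354 SD equals the whole critical difference.

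**Which program costs were shared in the trial.** Primary Hypothesis 2's neighbour, Primary Hypothesis 1, says every participating client completed the PDE and that the recommendation set was worked out for control clients as well. Client Participants lists counselors' obtaining of recommendations among the steps that define full enrolment, for all 140. The conditional wording in Primary Hypothesis 1 leaves it unclear whether control counselors saw the recommendations. So c cannot be read off as the difference in program use between the trial arms; it has to be defined against TAU without the tool, which is the comparator named in Primary Analytic Approach.

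**The case against.** The strongest reply is that the SAP states its scope openly: it costs services provided to clients, at reimbursement prices. For that quantity the omission is no bias. This is right, and it is why the defect lies in the label and the conclusion and not in the service-cost comparison as such. It does not rescue the Results sentence, which speaks of the program's cost effectiveness.

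Several stronger readings are tempting and are not supported:

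- *Program cost fell only on the experimental arm, so the difference is understated by exactly that cost.* The PDE and, read literally, the obtaining of recommendations took place in both arms. Only the part incremental to TAU counts.
- *Services or activities without a CPT code were priced at zero.* The SAP gives no other pricing rule, but it does not say that uncoded items were dropped.
- *All counselor time on recommendations is missing.* Some may fall inside sessions already priced by CPT code; adding it again would double count.
- *The bias can be put in dollars.* With assumed program costs of $50 to $200 per client, the share of the half-width is 14–56% at an assumed SD of $1,000, 28–113% at $500 and 5–19% at $3,000. Nothing in the SAP selects among these.
- *The omission produced a false claim.* The result was null, and no saving was claimed.

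It is also fair to say that adding program cost would not by itself turn a t-test on mean cost into a cost-effectiveness analysis, because cost and effect are never analysed jointly. That strengthens the case for relabelling.

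**Conclusion.** The point holds as a mismatch between what is costed and what is concluded. Following Primary Hypothesis 5 exactly yields a comparison of mean Medicare-priced service cost, which cannot support a statement on the cost effectiveness of BH-CDS against TAU. The direction is settled only on the condition that the program's incremental cost is positive: the estimate is then too low as a measure of the cost of using BH-CDS. The size is unknown and may be small. What can be calculated is the sensitivity: a half-width of 0.354 SD and a shift in t of 0.56 per omitted 0.1 SD, given a common SD and a constant program cost per client. The null result limits the harm to interpretation. It should not be read as equal total cost, and including a positive program cost would move the estimate against BH-CDS.

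**What to change.** 1. Relabel Primary Hypothesis 5 and its Results entry as a comparison of mean Medicare-priced service cost between arms, and draw no conclusion on the program's cost effectiveness from it. This needs no new data.
2. State how charted services without a CPT code were priced, since Primary Hypothesis 1 counts wraparound services and feeds the costing.
3. As a sensitivity analysis, add a low-to-high per-client BH-CDS cost, incremental to TAU, to every experimental client and repeat the comparison. Leave out counselor time already inside CPT-priced sessions. Report the difference with its 95% interval at each value.

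The cost is one bounded unit-cost assumption, a short re-analysis, and a figure somewhat less favourable to BH-CDS.
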